| | 
approximation, a sample size of 139, provides a two-sided 95% confidence interval for proportion of subjects not meeting the outcome of interest (liver transplantation and/or death) within a half width of 5% from the observed proportion at an expected proportion of 90%.
 |
| 
Statistical Methods
 | 
Demographic and Anamnestical Data:
 
All demographic and anamnestical data will be analyzed descriptively. For quantitative variables, the descriptive summary (means, medians, standard deviation, minimum and maximum) will be calculated. For qualitative data, the corresponding absolute and relative frequencies will be determined.
 
Efficacy Analysis:
 
The primary endpoint is the proportion of subjects treated with Legalon[®] SIL that do not exhibit morbidity (liver transplantation) and/or mortality (death).
 
Proportion of subjects not meeting outcome of interest (liver transplantation and/or death) will be determined. Furthermore, the corresponding 95% confidence intervals will be determined.
 
Sensitivity Analyses:
 
Subject survival rate without hepatic transplantation and/or death will be calculated for all subjects and for each stage of disease. Moreover, the corresponding 95% confidence intervals for the rate of survival will be determined. The survival time will be described by means of Kaplan-Meier estimates.
 
Secondary endpoint (efficacy):
 
 • All quantitative secondary endpoints will be analyzed descriptively. Means, medians, standard deviations, minimum and maximum will be calculated as measures of location and dispersion. • The time to normality for AST, ALT, bilirubin, PT/INR, and creatinine, if abnormal at presentation, will be determined for all subjects and for each stage of disease by means of Kaplan-Meier estimates. 
Additional summaries -- Assessment of Emergency Liver Transplantation Criteria in ALF due to Amanita Poisoning – using Ganzert’s and Escudie’s criteria. (13a.
 
 • Number (%) of subjects without hepatic transplantation by Ganzert’s intoxication (pre-treatment) • Elapsed days between amanita poisoning and start of treatment |

| | |

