¹ * All labs to be repeated if first dose occurs greater than 4 hours from last set of labs.

² ** If subject is diabetic, then follow institution's standard for glycemic monitoring.

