The second stage of amatoxin poisoning is characterized by generalized clinical improvement (resolution of gastrointestinal symptoms) that begins 24 to 48 hrs after ingestion, albeit masking the hepatic deterioration that is occurring at the same time. The liver function tests show a progressive elevation of transaminases and an evolving coagulopathy. Early renal damage may be reflected by elevations in the serum creatinine and blood urea nitrogen levels.

Grade 1: Patients develop gastroenteritis-like symptoms several hours (6-36) after ingestion but do not develop severe biochemical indications of hepatitis (peak transaminases <1000 without coagulopathy) or renal dysfunction.

Grade 2: In addition to GI symptoms patients manifest a moderate (1000-5000 IU/L) rise in transaminases and a moderate (peak INR <2.0) coagulopathy.

Stage III

Transition into the third stage can occur quite suddenly. Hepatic failure may be fulminant and is manifested by a severe increase in serum transaminases and profound coagulopathy. Patients may experience a swift progression from Stage I to Stage III or IV. The presence of hypoglycemia is a poor prognostic sign reflecting massive hepatic necrosis. Normalization of transaminases in the setting of a rising INR, creatinine, ammonia level plus worsening symptoms, should be considered to be a sign of fulminant hepatic necrosis and, hence an indicator of poor prognosis. Renal failure, due to hepatorenal syndrome and/or direct nephrotoxicity of amanitins, may result in severe oliguria or anuria. Fifty percent of patients with amatoxin poisoning may also have laboratory evidence of pancreatitis (2).

Grade 3: Patients develop a marked elevation of transaminases (>5000 IU/L) and significant coagulopathy (INR>2.0). Grade 3 is divided into two subgroups according to bilirubin values. In Grade 3a: hyperbilirubinemia is mild or absent, while Grade 3b: shows a steep and continuous rise in bilirubin (greater than 5 mg/dL).

Grade 4: A steep rise in transaminases is accompanied by a corresponding steep decline in clotting function (INR>3.0) and renal dysfunction.

Grade 1 and Grade 2 patients have the best chance of surviving amatoxin poisoning and need symptomatic treatment only. Grade 3, particularly Grade 3b patients, are at risk and should be

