transferred to a tertiary care center where liver transplant is available. Grade 4 patients have an extremely poor prognosis. There is a 90% probability of death in spite of intensive therapy. Survival usually requires a liver transplant.

Laboratory Abnormalities and Corresponding Prognostic Indication

Transaminases

Grade 1 patients show mild elevations of liver enzymes. Grade 2 patients develop a moderate rise in transaminases, usually below 5,000 IU/L but sometimes much higher. Grade 3 patients show a steep and massive rise in transaminases. There is no significant difference in the magnitude of transaminase results in Grade 4 relative to Grade 3, although in fatal cases the mean values are generally higher. A decrease of transaminase values on Day 4 is either a sign of improvement or a hepatic "burn-out" phenomenon. A massive rise in transaminases (Grade 3 and 4) does not necessarily predict a fatal outcome, whereas a mild rise in transaminases (Grade 2) generally indicates a good chance for survival.

Prothrombin Time

PT/INR is of high prognostic value. An early and steep prolongation of prothrombin time values suggests a poor prognosis. In Europe, those patients in whom prothrombin times could not be improved to values above 20-30% by substitution of clotting factors on Days 3-4 had >90% mortality. From 48 hrs after ingestion onwards, there is a significant difference between the prothrombin time of survivors in Grade 3 (>30 %) and non-survivors in Grade 4 (< 20%).

Bilirubin

On admission to the hospital, bilirubin values are normal in 90% of all cases. Elevation at this early stage (>3 mg/dL) suggests a poor prognosis. During the course of the intoxication, only about 20% of Grade 3 patients (Grade 3b) show a marked rise in bilirubin. It is possible to obtain information on the prognosis from the absolute values after Day 3. At that time, values < 5 mg/dL indicate a favorable prognosis, even if transaminases are high, while a value > 5 mg/dL indicates a severe or fatal course.

Impairment in kidney function

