3.2.2 Secondary Efficacy

Efficacy as demonstrated by time to normality of the laboratory values from start of treatment with Legalon® SIL. The laboratory values to be followed are transaminases and renal function tests (AST, ALT, bilirubin, PT/INR, creatinine, lactic acid).

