7.4 Secondary Endpoint (s)

The secondary endpoints of the study are:

- Proportion of patients not needing liver transplantation
- The time to normality for AST, ALT, bilirubin, PT/INR, and creatinine during the treatment period
- Number (%) of patients without hepatic transplantation by Ganzert's intoxication (pre-treatment)
- Elapsed days between amanita poisoning and start of treatment
- Number (%) of patients without hepatic transplantation by Ganzert's intoxication (during treatment)
- Number (%) of patients without hepatic transplantation by INR severity criteria (INR < 2 and ≥ 2) (during treatment)
- Number (%) of patients without hepatic transplantation by Escudie's intoxicion grade transplantation criteria (INR < 6 and ≥ 6) (during treatment)

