7.5 Statistical Analysis Methodology

In general, data will be summarized using descriptive statistics by treatment group. Continuous variables will be summarized using the mean, standard deviation, median, minimum value and maximum value. Categorical variables will be summarized using frequency counts and percentages. All data will be presented in patient data listings. Any data excluded from the summaries and statistical analyses will be flagged accordingly. Baseline value is defined as the last valid value prior to the treatment, i.e. in other words, Baseline value is treatment specific value. If the data is missing at Baseline, then the Baseline will be imputed with the corresponding value at screening. Detailed methodology for summary and statistical analyses of the data collected in this study will be documented in a Statistical Analysis Plan (SAP). This document may modify the plans outlined in the protocol; however, any major modifications of the primary endpoint definition and/or its analysis will also be reflected in a protocol amendment.

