7.5.7 Analysis of Secondary Endpoint(s)

All secondary analysis will be carried out using the Full Analysis Set.

The endpoints of proportion of patients not needing liver transplantation, without hepatic transplantation by Ganzert's intoxication (pre-treatment), without hepatic transplantation by Ganzert's intoxication (during treatment), without hepatic transplantation by INR severity criteria (INR < 2 and ≥ 2) (during treatment), without hepatic transplantation by Escudié's intoxication grade transplantation criteria (INR < 6 and ≥ 6) (during treatment) will be analyzed in the same way as the analysis of primary endpoint. The number and proportion of patients meeting the criteria will be computed and presented along with 95% CI that is computed using Newcombe-Wilson score method.

Elapsed days between amanita poisoning and start of treatment will be summarized descriptively.

The time to normality for AST, ALT, bilirubin, PT/INR, and creatinine will be analyzed using Kaplan-Meier estimation method of estimation for the survival time. 95% CI will be computed for the survival rate by using Greenwoods formula. The analysis of time to normality for AST, ALT, bilirubin, PT/INR, and creatinine will be analyzed by the disease severity stages as well.

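### Time to normality has no single risk set: the synopsis admits only markers abnormal at presentation, Sections 3.2.2, 7.4 and 7.5.7 state no limit, and under the synopsis rule patients who turn abnormal later are left out

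*Combined protocol and SAP*

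**What the plan says.** Four places describe the endpoint:

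- Synopsis, Statistical Methods: "The time to normality for AST, ALT, bilirubin, PT/INR, and creatinine, if abnormal at presentation, will be determined for all subjects", overall and by disease stage, with Kaplan-Meier estimates.
- Section 3.2.2: "Efficacy as demonstrated by time to normality of the laboratory values from start of treatment with Legalon® SIL". This sets the time origin and says nothing about which patients enter.
- Section 7.4: "The time to normality for AST, ALT, bilirubin, PT/INR, and creatinine during the treatment period". No entry condition.
- Section 7.5.7: "The time to normality for AST, ALT, bilirubin, PT/INR, and creatinine will be analyzed using Kaplan-Meier estimation method". The Full Analysis Set is used, with Greenwood intervals and a breakdown by severity stage. Again there is no entry condition.

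Two other passages bear on the anchor. Section 7.5 says "Baseline value is defined as the last valid value prior to the treatment". A footnote to the schedule in Section 1 says "All labs to be repeated if first dose occurs greater than 4 hours from last set of labs". The plan therefore expects values to change between arrival and first dose.

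None of these places says what happens to a marker that is normal on arrival and becomes abnormal later. None says how death or transplantation enters the curve.

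**The concern.** Section 2.2 describes an illness that often worsens after arrival. For bilirubin it says "On admission to the hospital, bilirubin values are normal in 90% of all cases", and it takes prognosis from the values after Day 3. For Stage II it says "The liver function tests show a progressive elevation of transaminases and an evolving coagulopathy", and Stage III brings a profound coagulopathy. Hepatorenal syndrome is described as a late event.

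A rule that admits a marker only if it was abnormal at presentation leaves out the patient who arrives with normal bilirubin and INR and then deteriorates. That patient's recovery, or failure to recover, is missing from the curve that is meant to describe recovery. Because the body sections do not repeat the rule, two analysts following different parts of the protocol could report different denominators and different medians from the same data.

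**Working it through.** **1. The plan's own figure.** The sample size is set by precision for the primary proportion: n = 1.96² × 0.90 × 0.10 / 0.05² = 138.29, rounded up to 139. The half-width at 139 is 1.96 × √(0.09/139) = 4.99%. This reproduces. No sample size or precision is given for time to normality, so 139 serves below only as the number of patients.

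**2. Who enters, by pattern of a single marker.**

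| At presentation | At baseline | On treatment | Synopsis | Sections 3.2.2, 7.4, 7.5.7 |
|---|---|---|---|---|
| abnormal | abnormal | any | in | in |
| normal | abnormal | any | out | not stated; has a recovery to time from start of treatment |
| normal | normal | abnormal | out | not stated |
| abnormal | normal | any | in, although already normal when the clock starts | not stated |
| normal | normal | normal | out | not stated |

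The second and fourth rows arise because presentation and baseline are different time points. Screening may last up to 24 hours (Synopsis), and drug is dispatched only after IRB approval (Section 6.1).

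**3. Size for bilirubin under the synopsis rule.** Inputs are N = 139 and 90% normal on admission (Section 2.2). The 90% refers to all cases. Trial patients must already have a raised AST or ALT (Section 4.3.1), so applying it to them is an assumption.

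- Analysed: 139 × 0.10 = 13.9, about 14. Not analysed: 139 × 0.90 = 125.1, about 125.
- If 5% or 20% were abnormal instead: 139 × 0.05 = 7, or 139 × 0.20 = 28.
- Widest 95% half-width for a proportion, 1.96 × √(0.25/n): about ±26 points at n = 14 (±37 at 7, ±19 at 28), against ±8.3 points at n = 139. The further split by stage makes this thinner.

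**4. How many of the relevant patients are lost.** The 125 are those normal on admission. Patients who never become abnormal have no recovery to time and are properly outside the curve. The loss that matters is those who become abnormal later, and the documents do not give that number. Section 2.2 says about 20% of Grade 3 patients have a marked bilirubin rise but gives no share of patients in Grade 3. As an assumption only, let a share g of the 125 turn abnormal. The share of all ever-abnormal patients who are left out is then 125g / (125g + 14):

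| g | Later abnormal | Left out of the ever-abnormal |
|---|---|---|
| 5% | 6.25 | 31% |
| 10% | 12.5 | 47% |
| 20% | 25 | 64% |
| 30% | 37.5 | 73% |

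**5. Other markers.**

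- INR: Section 2.2 describes evolving coagulopathy but gives no share normal on arrival, so the support is qualitative.
- Creatinine: Section 2.2 calls prerenal azotemia at presentation common and reports an early rise in about 70% of fatal cases. Many affected patients may therefore already be abnormal on arrival, and the support is weak.
- AST and ALT: at least one must be raised at entry, so they are little affected.

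**The case against.** The strongest reply is that worsening on treatment is recorded elsewhere.

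- Section 3.2.1.1 follows changes from baseline in these same markers.
- Section 7.7.4 plans summaries by time point and baseline shift tables, and the synopsis adds frequencies inside and outside the reference ranges.
- Sections 7.4 and 7.5.7 report outcomes by on-treatment INR (below 2 or not, below 6 or not).
- Clinically significant laboratory changes are recorded as adverse events.
- The primary endpoint counts transplantation and death.

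All of that stands. A reader might infer that deterioration is hidden or that the trial cannot show failure of prevention. The documents do not support either inference. Time to normality measures recovery, and restricting it to patients with something to recover from is a conventional choice. What these tables do not give is the time to recovery of patients who became abnormal after arrival.

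A reader might also infer that, under the body sections, a marker normal at baseline counts as an immediate success, so that the bilirubin curve would start near 90%. No passage says so. The inference rests on silence, the synopsis points the other way, and Section 7.5 leaves detailed methods to a SAP. The 90% also refers to admission, not to start of treatment.

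It is also fair to object that 125 of 139 is not a count of patients who worsen, and that creatinine is often raised early. Both objections stand, and the conclusion is limited accordingly.

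**Conclusion.** The concern holds in a limited form. The synopsis and Sections 3.2.2, 7.4 and 7.5.7 do not define the same risk set, and presentation is not the point at which the clock starts. Under the synopsis rule, a patient whose bilirubin or INR is normal on arrival and abnormal later is never in that marker's analysis.

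For bilirubin, about 14 of 139 patients would be analysed if the 90% background figure applied to trial patients, or 7 to 28 if 5% to 20% were abnormal on arrival. How many patients worsen after a normal value is unknown, so the effect on the reported times cannot be sized from the documents. The case is qualitative for INR and weak for creatinine.

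The defect affects one descriptive secondary endpoint and leaves the primary conclusion untouched. It should still be corrected before analysis, because the choice of rule changes who is counted.

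**What to change.** State one rule, in the same words, in the synopsis and Sections 3.2.2, 7.4 and 7.5.7:

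1. **Main curve.** For each marker, include patients abnormal at baseline (the last pre-treatment value, as Section 7.5 defines it), timed from start of treatment. The event is the first normal value with no later recorded abnormal value. State which draws count, because Section 7.4 mentions only the treatment period. Treat death and transplantation as competing events, not ordinary censoring, and report cumulative incidence. These events are not rare: 8 of the first 50 patients in Section 7.6 had one.
2. **Patients normal at baseline.** Do not count them as events. Report the number and percentage who become abnormal on treatment and the peak value. For these patients, give time to sustained normality from the first abnormal value. Putting them in the main curve from start of treatment would credit them with time at risk during which the event could not happen (immortal time).
3. **Never abnormal.** Report as a separate count.

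The cost is wording in four places and one extra table. Bilirubin, PT, INR and creatinine are already required daily on treatment (Section 6.3.1), so no new data are needed. The picture of recovery may be less favourable, though the documents do not allow the direction or size to be predicted with certainty.

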| | 
More than 90% of all fatal mushroom poisonings worldwide are due to amatoxin containing species that grow abundantly in Europe, South Asia, and the Indian subcontinent. Many cases have also been reported in North America (1,2,3). Initial symptoms of abdominal cramps, vomiting, and a severe cholera-like diarrhea generally do not manifest until at least six to eight hours following ingestion and can be followed by renal and hepatic failure. Outcomes range from complete recovery to fulminant organ failure and death which can sometimes be averted by liver transplant.
 
Epidemiological data on mushroom poisoning, particularly poisoning with amatoxin-containing mushrooms, are rare. The true incidence of this intoxication is unknown since national data banks maintained at poison control centers have only incomplete data of this non-reportable illness [4].
 
Uncontrolled European studies and emergency use in the USA, suggest that treatment of amatoxin poisoning with Legalon® SIL drug may prevent severe morbidity (hepatic failure) and mortality.
 
This is a Phase II Multi-Center Open-Label Clinical Trial to Assess the Prevention of Liver Transplantation and/or Death Among Subjects Treated with Intravenous Silibinin (Legalon® SIL) for Amatoxin Induced Hepatic Failure. A total of 139 subjects will be enrolled into this study.
 
Legalon® SIL is formulated as a sterile lyophilisate in rubber-stoppered vials to be dissolved for intravenous infusion, containing 528.5 mg silibinin-C-2',3-dihydrogen succinate, disodium salt which is equivalent to 350 mg of silibinin according to DNPH testing or 315 mg of silibinin according to HPLC determination. The recommended daily dose is 20 mg silibinin/kg via continuous infusion over 24 hours, following a single loading dose of 5 mg silibinin/kg on the first day of treatment.
 
Subjects will be screened for eligibility and, if confirmed to meet the study criteria, will be enrolled to receive treatment of Legalon® SIL.
 
The study is comprised of a screening period of up to 24 hours from the time a potential study participant is identified. Treatment may be administered for up to 96 hours, or longer, following consultation with PPI. The final study assessment (Follow-up Visit) is to occur at 10 (+/-2) days from the last administered treatment. During screening, treatment and follow-up, assessments for medical history (only at screening), vital signs, labs and physical examination will be completed. Concomitant medications and adverse events will be recorded on every subject from the time of consent through the completion of the Follow-up Visit. Sponsor should be notified of any SAEs reported to the site and up to 30 days after discontinuation of study medication.
 |

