Early renal dysfunction signals a poor prognosis. Prerenal azotemia secondary to dehydration on initial presentation is a common finding that can usually be reversed by aggressive fluid replacement. Acute tubular necrosis may also occur in severely dehydrated patients and may represent a direct cytotoxic effect of amatoxin. A slight elevation of creatinine on Days 1 to 2 that does not respond to fluid replacement suggests that a direct toxic effect has occurred. About 70% of fatal cases show this early increase of creatinine. Hepatorenal syndrome occurs later and indicates an extremely poor prognosis.

In summary, Legalon® SIL will be administered to patients with amatoxin poisoning diagnosed by history, gastrointestinal symptoms, elevated liver enzymes. Treatment will consist of a 5 mg/kg loading dose followed by 20 mg/kg/day via continuous infusion (13). The treating physician is expected to administer supportive therapy of his/her choosing but consistent with best practices. Legalon® SIL will be discontinued when coagulopathy is no longer present, and when liver function tests have returned to no greater than 2 times the upper limit of normal or patient does not respond to treatment with Legalon® SIL. Patients will be followed 10 (+/-2) days after the end of Legalon® SIL therapy with follow-up laboratory studies and physical exam. If the Follow-up Visit is not feasible due to patient's

condition, reason for the missed visit must be clearly documented in the patient's medical record.

Complete information for Legalon® SIL may be found in the Legalon® SIL Investigator's Brochure.

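### Time to normality has no consistent risk set: the synopsis selects on the presentation value, the clock starts at first dose, and the body sections set no abnormality condition

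*Combined protocol and SAP*

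**What the plan says.** The synopsis (Statistical Methods, secondary endpoint) puts a marker into the analysis by its value on arrival: "The time to normality for AST, ALT, bilirubin, PT/INR, and creatinine, if abnormal at presentation, will be determined for all subjects".

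Section 3.2.2 sets the time origin: "Efficacy as demonstrated by time to normality of the laboratory values from start of treatment with Legalon® SIL". It does not say which markers are at risk.

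Section 7.4 sets the window, again without an abnormality condition: "The time to normality for AST, ALT, bilirubin, PT/INR, and creatinine during the treatment period". Section 7.5.7 specifies Kaplan-Meier estimation on the Full Analysis Set, overall and by severity stage. It too has no abnormality condition, and it gives no rule for a marker that is already normal when the clock starts.

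Presentation and first dose are distinct time points. Table 1 has one column for each, with creatinine in both, and its footnote says: "All labs to be repeated if first dose occurs greater than 4 hours from last set of labs". The synopsis adds: "The study is comprised of a screening period of up to 24 hours from the time a potential study participant is identified". Under Section 6.1 the drug is dispatched only after IRB approval has been received.

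Section 7.5 defines a baseline that would fit this endpoint: "Baseline value is defined as the last valid value prior to the treatment". If that value is missing, the screening value is used. No section links the time-to-normality analysis to it.

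**The concern.** A time-to-event analysis needs each subject to be free of the event when the clock starts. Here the synopsis checks that at one time point and Section 3.2.2 starts the clock at a later one. In between, the patient receives supportive care chosen by the treating physician.

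For creatinine the protocol itself supplies the mechanism, in the Section 2.2 text on kidney function: "Prerenal azotemia secondary to dehydration on initial presentation is a common finding that can usually be reversed by aggressive fluid replacement". Take a patient whose creatinine is raised at presentation and normal on the pre-dose repeat, while the transaminases are still rising. That patient is in the synopsis risk set and already meets the endpoint at first dose. The recovery would then be read as part of the efficacy of a drug that had not yet been given. The trial has a single arm, so no control group carries the same early step.

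**Working it through.** **The plan's own figures.** The documents state no number for this endpoint. The only related figure is the sample size for the primary proportion: n = 1.95996² × 0.90 × 0.10 / 0.05² = 138.29, rounded up to 139. It reproduces, and nothing below changes it.

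**Step 1: classify a marker by its two pre-treatment values.**

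| At presentation | Last pre-dose value | Synopsis condition | No condition (Sections 3.2.2, 7.4, 7.5.7) | Baseline condition |
|---|---|---|---|---|
| abnormal | abnormal | at risk | at risk | at risk |
| abnormal | normal | included, event already met | included, event already met | not at risk, reported separately |
| normal | abnormal | left out | at risk | at risk |
| normal | normal | left out | included, event already met | not at risk |

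The synopsis wording misplaces rows 2 and 3. The body wording misplaces rows 2 and 4. Only the baseline condition starts with markers that are all abnormal at time zero.

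**Step 2: see which markers the existing rules protect.** Section 4.3.4 withdraws subjects whose laboratory values indicate recovery before the drug. Section 6.3 requires that the patient still be eligible when the drug arrives, and the laboratory criterion in Section 4.3.1 is AST or ALT above the upper limit of normal. These rules mainly cover the transaminases. They do not reach a creatinine that normalises while AST or ALT stays raised.

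**Step 3: row 3, with the one relevant figure in the documents.** Section 2.2 says that bilirubin is normal on admission in 90% of cases. If trial subjects resemble those cases (assumption), the synopsis condition would admit about 0.10 × 139 = 14 subjects to the bilirubin analysis. The others would be left out even if bilirubin had become abnormal by first dose.

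**Step 4: row 2, illustration only.** Let f be the share of the analysed markers already normal at first dose. The documents do not give f. Let F(t) be the proportion normal by time t among markers still abnormal at first dose.

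- Reported proportion normal by t = f + (1 − f) × F(t), so the curve steps by f at or near time zero.
- If recovery is exponential with median M (assumption), reported median / M = log2(2(1 − f)) for f < 0.5, and 0 for f ≥ 0.5.
- With M = 48 hours (assumption), F(24 h) = 1 − 2^(−0.5) = 29.3%.

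| f (assumed) | Reported median / M | Reported median if M = 48 h | Reported normal by 24 h (29.3% without the step) |
|---|---|---|---|
| 5% | 0.93 | 44.4 h | 32.8% |
| 10% | 0.85 | 40.7 h | 36.4% |
| 20% | 0.68 | 32.5 h | 43.4% |
| 30% | 0.49 | 23.3 h | 50.5% |
| 50% | 0 | 0 h | 64.6% |

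Scoring these markers at the first 6-hourly draw instead of at time zero gave the same simulated medians for f = 10% to 30%. This is expected, because the median then lies beyond 6 hours in either case.

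**The case against.** The strongest reply is that the plan never says such markers are scored as recoveries at time zero. No event rule is written, the presentation condition stands only in the synopsis, and Section 7.5 leaves detailed methods to a SAP. This stands as a limit on the claim. A reader might infer that the plan fixes the risk set at presentation and credits these recoveries to the drug. The documents support only that its sections disagree and that a literal reading would lead there. It does not remove the problem: the body wording, with no condition, has a defect of its own (row 4), and no rule in the available text settles the matter.

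A second reply is that few markers are affected. This largely stands. Transaminases are mostly protected, bilirubin is seldom abnormal on admission, and Section 2.2 describes a coagulopathy that evolves rather than resolves in the second stage. Creatinine remains as the clear case for row 2.

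A third reply is that the mechanism is not quantified. Section 2.2 gives no time frame for the reversal, and the same paragraph describes creatinine rises that do not respond to fluids. The 24 hours is a maximum for screening, not a stated interval from presentation to dose. If the presentation values are under 4 hours old at first dose and are not repeated, they are the baseline and no mismatch arises. All of this stands, and it is why no size can be given.

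Finally, supportive care continues after dosing, so a corrected risk set would still not isolate a drug effect. That is true. The correction removes only what happened before the drug.

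**Conclusion.** The point holds as an inconsistency in the risk set of a secondary endpoint. The synopsis selects on the presentation value, Section 3.2.2 counts from first dose, and Sections 7.4 and 7.5.7 select on nothing. Read literally, the synopsis would count some pre-drug normalisations, chiefly of creatinine, as recoveries at or near time zero, and would leave out markers that become abnormal before dosing. The body wording could count markers that were never abnormal.

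The size is unknown, because f is not in the documents. The table above rests on assumed values of f, exponential recovery and an assumed 48-hour median. A reader might infer that the median time to creatinine normality will fall to zero. That would need at least half of the analysed creatinine values to be normal already at first dose, and nothing in the documents shows this.

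The endpoint is descriptive and carries no test. The primary endpoint, its confidence interval and the sample size of 139 are unaffected. It is worth correcting because the endpoint is presented as evidence of efficacy in a trial without a control arm.

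**What to change.** Use one definition throughout. In the synopsis, replace the condition on the presentation value with abnormality at baseline, meaning the last valid value before first dose as defined in Section 7.5. Add the same condition to Sections 3.2.2, 7.4 and 7.5.7, which have none at present, and state in each that time runs from first dose. For each marker, report separately the number that were abnormal at presentation and normal at baseline, as normalised before study drug and not as events.

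The cost is one sentence in each of four places. The schedule already collects the pre-first-dose values, and Section 7.5 already provides a fallback when baseline is missing. The downside is that the creatinine risk set may shrink and its curve may look less favourable. Compared with the synopsis wording, the bilirubin or INR risk set may grow, because markers that became abnormal between presentation and first dose would now be included.
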